Primary Objective: Determine the efficacy of 3 doses of VGX-3100 with respect to combined histopathologic regression of anal or anal/peri-anal HSIL and virologic clearance of HPV-16 and/or HPV-18.
Primary Endpoint: Proportion of subjects with no histologic evidence of anal or anal/peri-anal HSIL ⁶ on histology (i.e., collected via biopsy or excisional treatment) ⁷ and no evidence of HPV-16/18 at Week 36 from intra-anal and/or peri-anal lesion tissue ⁸ .

¹ High-grade Squamous Intraepithelial Lesion

² Grade 2 Anal Intraepithelial Neoplasia

³ Grade 3 Anal Intraepithelial Neoplasia

⁴ Grade 2 Peri-anal Intraepithelial Neoplasia

⁵ Grade 3 Peri-anal Intraepithelial Neoplasia

⁶ No evidence of anal or anal/peri-anal HSIL is defined as normal tissue or anal or anal/peri-anal LSIL.

⁷ A treatment responder is defined as a subject with no histologic evidence of anal or anal/peri-anal HSIL and no evidence of HPV-16 or HPV-18 in anal lesion tissue and who did not receive any non-study treatment of curative intent of intra-anal and/or peri-anal lesions. A treatment non-responder is defined as a subject with histologic evidence of anal or anal/peri-anal HSIL, adenocarcinoma-in-situ (AIS), anal or anal/peri-anal carcinoma or a subject with evidence of HPV-16/18 in anal lesion tissue or a subject who received non-study treatment of curative intent of intra-anal and/or peri-anal lesions.

⁸ An intra-anal and/or peri-anal lesion evaluated by the Pathology Adjudication Committee (PAC).

Secondary Objectives	Associated Secondary Endpoints
1. Evaluate the safety and tolerability of VGX-3100 delivered IM followed by EP	1a. Local and systemic events for 7 days following each dose as noted in the Participant Diary Card (PDC). 1b. All adverse events including SAEs, UADEs, and other unexpected AEs for the duration of the study (through the Week 88 visit)
2. Determine the efficacy of three doses of VGX-3100, as measured by histologic regression of anal or anal/peri-anal HSIL	2. Proportion of subjects with no evidence of anal or anal/peri-anal HSIL on histology (e.g. biopsies or excisional treatment) at Week 36
3. Determine the efficacy of three doses of VGX-3100 as measured by virologic clearance of HPV-16 and/or HPV-18 by testing from lesion tissue	3. Proportion of subjects with no evidence of HPV-16 and/or HPV-18 ⁹ from intra-anal and/or peri-anal tissue by type specific HPV testing at Week 36

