¹² An intra-anal and/or peri-anal lesion which is confirmed to be HPV-16 and/or HPV-18 positive and have histologically confirmed anal or anal/peri-anal HSIL evaluated by the Pathology Adjudication Committee (PAC).

¹³ Baseline photographic imaging is defined as photographs obtained pre-biopsy at Screening, or post biopsy at Screening (for subjects with historical biopsy tissue).

Exploratory Objectives	Associated Exploratory Endpoints
1. Describe the long term efficacy of VGX-3100 with respect to combined histopathologic regression of anal or anal/peri-anal HSIL and virologic clearance of HPV-16 and/or HPV-18	1. Proportion of subjects with no histologic evidence of anal or anal/peri-anal HSIL on histology (i.e. collected via biopsy or excisional treatment) and no evidence of HPV-16/18 at Week 64 by testing from intra-anal and/or peri-anal lesion tissue
2. Describe the long term efficacy of VGX-3100, as measured by histologic regression of anal or anal/peri-anal HSIL	2. Proportion of subjects with no evidence of anal or anal/peri-anal HSIL on histology (i.e. biopsies or excisional treatment) at Week 64
3. Describe the long term efficacy of VGX-3100, as measured by virologic clearance of HPV-16 and/or HPV-18 by testing from lesion tissue	3. Proportion of subjects with no HPV-16/18 at Week 64 by testing from intra-anal and/or peri-anal lesion tissue
4. Describe the long term efficacy of VGX-3100, as measured by virologic clearance of HPV-16 and/or HPV-18 by intra-anal swab testing	4. Proportion of subjects with no evidence of HPV-16 and/or HPV-18 from intra-anal swab by specific HPV testing at Week 64 and Week 88
5. Evaluate tissue immune responses to VGX-3100 in intra-anal and/or peri-anal samples	5. Assessment of proinflammatory and immunosuppressive elements in tissue, where feasible ¹⁴
6. Describe the clearance of HPV-16 and/or HPV-18 infection from non-anal anatomic locations	6. Proportion of subjects who have cleared HPV-16 and/or HPV-18 on specimens from non-anal anatomic locations as applicable based upon gender (i.e. oropharynx, cervical, vaginal, and penile at Week 36)
7. Describe the association of microRNA (miRNA) profile, previous anoscopy, cytology and HPV testing results with Week 36 histologic regression	7. HRA, cytology, and HPV test results and miRNA profile (baseline and at the Weeks 15 and 36) in conjunction with histologic regression of anal or anal/peri-anal HSIL at Week 36

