Pre-biopsy High Resolution Anoscopy Finding	Minimally required procedure
No lesion	Punch biopsy and photography; biopsy should be collected from within the approximate original boundaries of the study entry HSIL as proximal as possible to the original biopsy site which was previously determined to be HSIL by the PAC. New lesions or lesions that did not qualify at baseline should be biopsied at evaluation.
Single lesion (which was also present at baseline)	Punch biopsy and photography; biopsy should be collected within the boundaries of the original lesion and from the area most suspicious for advanced disease within the lesion by clinical exam. New lesions or lesions that did not qualify at baseline should be biopsied at evaluation.
Multiple lesions	Punch biopsies and photography; biopsy should be collected from the same lesions diagnosed as HSIL from study entry and from the area most suspicious for advanced disease within the lesion by clinical exam. New lesions or lesions that did not qualify at baseline should be biopsied at evaluation.

If HSIL is diagnosed in any Week 36 biopsy, but there is a reduction in the number of intra-anal and/or peri-anal lesion(s), reduction in peri-anal lesion(s) size or no change in peri-anal lesion(s) size from baseline (defined by Subgroup C), the Investigator has the option to administer a 4th dose of VGX-3100 at Week 40, and the subject will continue on the study to have HRA and biopsy at Week 64 of all lesions (qualifying and any other visible), i.e. the second efficacy checkpoint. Alternatively, the Investigator may instead choose to treat the subject with standard of care treatment (i.e. electrocautery, ablation, surgical excision), and the subject will continue on the study without further biopsy unless it is part of standard of care.

In the event of worsening anal or anal/peri-anal HSIL at any time during the trial (defined as any increase in lesion(s) area from baseline or worsening of anal or anal/peri-anal HSIL to cancer), the subject may receive standard of care treatment (i.e. electrocautery, ablation, surgical excision) per the Investigator's judgment but will continue on the study through Week 88 with HRA, but without further biopsy unless it is part of the standard of care.

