Data Safety & Monitoring Board (DSMB): An independent DSMB will meet quarterly to review safety data and tissue regression and viral clearance results. The DSMB will be charged with advising the Sponsor if there appears to be a safety issue. No formal interim analysis is planned. Refer to Section 3.8 for stopping rule criteria.

Definition of Responder and Non-Responder:

Responder and non-responder definitions (**Table 2 through Table 7**) take into account both histopathologic regression of anal or anal/peri-anal HSIL **and** virologic (HPV-16/18) clearance as measured by intra-anal and/or peri-anal tissue, since HPV persistence is an important factor in the clinical progression of HSIL. Any case of histologically confirmed progression from HPV-16/18 positive anal or anal/peri-anal HSIL to carcinoma according to the PAC is considered a non-responder.

Table 2: Definition of Responder and Non-Responder for Composite Endpoint of Regression and Clearance	
Responder	Non-Responder
No histologic evidence of anal or anal/peri-anal HSIL AND Negative PCR for HPV-16 or HPV-18 in anal lesion tissue AND No non-study treatment of curative intent of intra-anal and/or peri-anal lesions	Histologic evidence of anal or anal/peri-anal HSIL, anal Adenocarcinoma-in-situ (AIS), anal or anal/peri-anal carcinoma OR PCR positive for HPV-16 or HPV-18 in anal lesion tissue OR Any non-study treatment of curative intent of intra-anal and/or peri-anal lesions

Table 3: Definition of Responder and Non-responder for HSIL Regression Endpoint

Responder	Non-Responder
No histologic evidence of anal or anal/peri-anal HSIL 
AND
 No non-study treatment of curative intent of intra-anal and/or peri-anal HSIL	Histologic evidence of anal or anal/peri-anal HSIL or carcinoma at evaluation 
OR
 Any non-study treatment of curative intent of intra-anal and/or peri-anal HSIL

Table 4: Definition of Responder and Non-responder for Viral Clearance Endpoint

Responder	Non-Responder
No evidence of HPV-16 or HPV-18 in tissue/swab at evaluation 
AND
 No non-study treatment of curative intent of intra-anal and/or peri-anal HSIL	Evidence of HPV-16 or HPV-18 in tissue/swab at evaluation 
OR
 Any non-study treatment of curative intent of intra-anal and/or peri-anal HSIL

Table 5: Definition of Responder and Non-responder for Complete HSIL Regression Endpoint

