Responder	Non-Responder
No histologic evidence of anal or anal/peri-anal HSIL or LSIL 
AND
 No non-study treatment of curative intent of intra-anal and/or peri-anal HSIL	Histologic evidence of anal or anal/peri-anal LSIL, HSIL or anal or anal/peri-anal carcinoma at evaluation 
OR
 Any non-study treatment of curative intent of intra-anal and/or peri-anal HSIL

Table 6: Definition of Responder and Non-responder for Disease Non-Progression Endpoint

Responder	Non-Responder
No histologic evidence of a worsening anal or anal/peri-anal condition to anal or anal/peri-anal cancer relative to baseline	Histologic evidence of worsening of anal or anal/peri-anal condition to anal or anal/peri-anal cancer relative to baseline
AND	OR
No non-study treatment of curative intent of intra-anal and/or peri-anal HSIL	Any non-study treatment of curative intent of intra-anal and/or peri-anal HSIL

Table 7: Definition of Responder and Non Responder for Endpoint of Regression or Clearance

Responder	Non-Responder
No histologic evidence of anal or anal/peri-anal HSIL on histology	Histologic evidence of anal or anal/peri-anal HSIL on histology
OR	AND
No evidence of HPV-16 and/or HPV-18 intra-anal and/or peri-anal lesion tissue	Evidence of HPV-16/18 intra-anal and/or peri-anal lesion tissue
AND	OR
No non-study treatment of curative intent of intra-anal and/or peri-anal HSIL	Any non-study treatment of curative intent of intra-anal and/or peri-anal HSIL

Study Population:

Inclusion:

1. Must understand, agree and be able to comply with the requirements of the protocol and be able to provide voluntary consent to participate and sign an Informed Consent Form (ICF) prior to study-related activities;
2. Age 18 years and above;
3. Negative screening test for HIV-1/2^a within 30 days of Dose 1;
4. Confirmed anal or anal/peri-anal HPV-16 and/or HPV-18 infection at Screening by PCR from HSIL specimen;
5. Anal tissue (blocks only) provided to the Study Pathology Adjudication Committee (PAC) for diagnosis must be collected within 10 weeks of first dose of VGX-3100;
6. At least one anal or anal/peri-anal (AIN2/3 and/or PAIN2/PAIN3) lesion that is histologically-confirmed as HSIL by the PAC at Screening;
 - a. The lesion needs to be large enough to biopsy, but the biopsy (≥ 4 mm) should not remove the entire lesion in order to allow for continued lesion measurement while on the study;

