8.5 DESCRIPTION OF STATISTICAL METHODS

8.5.1 PRIMARY ANALYSES

The true treatment effect on the primary endpoint is p , where p denotes the true population probability of the primary endpoint. The primary hypothesis of superiority is: $H_0: p \leq 0.15$ vs. $H_1: p > 0.15$.

A p-value for this hypothesis test and corresponding 95% confidence interval will be computed based on the exact method of Clopper-Pearson. Superiority will be concluded if the one-sided p-value is <0.05 and the corresponding lower bound of the one-sided 95% CI exceeds 0.15.

For the analysis, the efficacy time frame is defined by any time starting from 14 days prior to the specified visit week.

The endpoint will be analyzed in two ways: a) based on all lesions and b) based on qualifying and new lesions.

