8.5.2 SECONDARY ANALYSES

The secondary efficacy binary endpoints will be analyzed in the same manner as the primary hypothesis, but without the hypothesis test p-values. The efficacy time frame is defined in the same manner as for the primary endpoint. All of the efficacy binary endpoints will be analyzed in two ways: a) based on all lesions and b) based on qualifying and new lesions.

The anatomic extent endpoint will be analyzed by calculating the mean percent change in surface area and the mean percent change in number of lesions and associated 95% t-distribution based confidence intervals.

Post-baseline increases in Flow responses will be summarized with medians and 95% CIs. Valid samples for statistical analysis purposes will be those collected within 14 days of the specified visits. Baseline is defined as the last measurement prior to the first treatment administration.

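### Lesion set (b) omits baseline lesions that did not qualify, so it can pass subjects who fail the protocol's own endpoint definition, and neither lesion set is named as decisive

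*Protocol*

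**What the plan says.** All references are to Protocol Version 3.0.

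- **Lesion sets.** Section 8.5.1 says of the primary endpoint: "The endpoint will be analyzed in two ways: a) based on all lesions and b) based on qualifying and new lesions". Section 8.5.2 extends this: "All of the efficacy binary endpoints will be analyzed in two ways: a) based on all lesions and b) based on qualifying and new lesions". Section 8.5.9 repeats it for the exploratory endpoints.
- **Qualifying lesion.** Synopsis footnote 12 defines it as "An intra-anal and/or peri-anal lesion which is confirmed to be HPV-16 and/or HPV-18 positive and have histologically confirmed anal or anal/peri-anal HSIL", as evaluated by the Pathology Adjudication Committee (PAC). The footnote gives no date.
- **Lesion classes at a biopsy visit.** Table 1 adds in each row: "New lesions or lesions that did not qualify at baseline should be biopsied at evaluation". Section 6.19 applies Table 1 to Weeks 36 and 64.
- **Endpoint tissue.** Footnote 8 takes any anal or peri-anal lesion that the PAC has evaluated.
- **Non-response.** The histology limb of Table 2 reads "Histologic evidence of anal or anal/peri-anal HSIL, anal Adenocarcinoma-in-situ (AIS), anal or anal/peri-anal carcinoma". The other limbs are HPV-16/18 by PCR in lesion tissue, and curative treatment outside the study. None is restricted by lesion class, and footnote 7 agrees.
- **Non-progression.** The responder side of Table 6 reads "No histologic evidence of a worsening anal or anal/peri-anal condition to anal or anal/peri-anal cancer relative to baseline", joined to a treatment limb that mentions only treatment of HSIL.
- **Decision rule.** Section 8.3 tests p ≤ 0.15 against p > 0.15. Section 8.5.7 sets multiplicity aside because one hypothesis is tested. No section says whether set (a) or set (b) provides that test.

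**The concern.** Table 1 recognises three kinds of lesion at evaluation: those that qualified at baseline, new ones, and those that were there at baseline but did not qualify. Set (b) names only the first two. The third kind includes, for example, Screening LSIL and Screening HSIL that was PCR-negative for HPV-16/18.

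If such a lesion carries HPV-16/18 HSIL at Week 36, the finding is a failure when the site is called new and is ignored in (b) when the site is called old. The protocol does not define a new lesion, and the trial is open-label.

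At stake is whether a superiority claim can rest on a response rate that departs from the endpoint in footnotes 7 and 8 and Table 2. The departure has one direction: set (b) uses a subset of the lesions in (a), so it can only raise the response proportion.

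**Working it through.** **1. Which lesions count**

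| Lesion at evaluation | Footnote 8 and Table 2 | Set (a) | Set (b) |
|---|---|---|---|
| Qualifying at baseline | counts | counts | counts |
| New | counts | counts | counts |
| Present at baseline, not qualifying | counts | counts | does not count |

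**2. One subject through the rules.** Suppose that the qualifying lesions have cleared, no new lesion is positive, and an old non-qualifying lesion shows HPV-16/18 HSIL at Week 36.

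- Table 2, footnote 7 and set (a): non-responder, because HSIL and HPV-16/18 are present in PAC-evaluated tissue.
- Set (b): that lesion is not read, so the subject is a responder unless another rule intervenes.
- Treatment limb of Table 2: it need not apply. For Subgroup C the synopsis lets the investigator give a fourth dose, which is study treatment.
- Section 7.1 classes subjects with an unscheduled biopsy as non-responders. The Week 36 biopsy is scheduled, so this rule does not apply either.

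**3. The plan's own figure.** Section 8.6 gives N = 24, a rate of 0.40 against 0.15, 90% evaluable and about 80% power. Section 8.5.1 gives an exact test at one-sided 0.05. Let r be the smallest count with P(X ≥ r | n, 0.15) < 0.05, where P(X ≥ r | n, p) = Σ C(n,k) p^k (1−p)^(n−k) for k = r to n. The evaluable number is 24 × 0.9 = 21.6.

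| n | r | Attained alpha | Power at 0.40 |
|---|---|---|---|
| 21 | 7 | 0.0287 | 0.800 |
| 22 | 7 | 0.0368 | 0.842 |
| 24 | 8 | 0.0199 | 0.808 |

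Averaged over a Binomial(24, 0.9) evaluable number, power is 0.815. The stated figure reproduces.

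**4. One subject at the boundary**

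| n | Responders | One-sided p | Lower 95% bound |
|---|---|---|---|
| 22 | 6 | 0.0999 | 0.126 |
| 22 | 7 | 0.0368 | 0.160 |
| 24 | 7 | 0.0572 | 0.146 |
| 24 | 8 | 0.0199 | 0.178 |

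**5. If (b) carries the claim.** Every responder under (a) is also a responder under (b), and every subject has at least one qualifying lesion, so the denominators match. Accepting success in either set is therefore the same as deciding on (b). Let the rate under (a) be 0.15 and let a further share d pass only under (b). The documents give no value for d; 2% to 10% is an assumed range. The chance of declaring superiority is P(X ≥ r | n, 0.15 + d).

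| d | n = 22, r = 7 | n = 24, r = 8 |
|---|---|---|
| 0 | 0.037 | 0.020 |
| 2% | 0.066 | 0.039 |
| 5% | 0.133 | 0.089 |
| 10% | 0.301 | 0.234 |

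**6. Carcinoma in an old non-qualifying lesion.** Section 8.5.2 applies set (b) to non-progression too, so (b) would not read the lesion. The treatment limb of Table 6 covers treatment of HSIL only. The sentence above Table 2 that makes carcinoma a non-response covers progression from HPV-16/18-positive HSIL, which by definition a non-qualifying lesion was not. Nothing explicit closes this gap.

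**The case against.** Several points on the other side have force.

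- **Set (a) is reported beside (b)** for every binary efficacy endpoint and already matches footnote 8 and Table 2. This stands: no failure disappears from the report. It does not settle which set decides superiority.
- **Footnote 12 is undated**, so an old lesion found to be HPV-16/18 HSIL at Week 36 could be said to qualify then. The wording allows this, but Table 1 ties qualification to baseline. Even on the undated reading, an old lesion that is HPV-16/18 positive without HSIL stays outside (b), although Table 2 counts it as failure.
- **Week 36 sampling is uncertain.** The synopsis and Sections 3.0, 3.7 and 6.17 direct Week 36 biopsies to Screening HSIL sites and add all other visible lesions only at Week 64. This stands and limits how often the case arises at Week 36. It does not remove it, because Screening HSIL that was HPV-16/18 negative is re-biopsied on either reading. Placing lesions under 4 mm in the third class is an inference.
- **Relabelling is constrained.** Lesions of at least 4 mm are biopsied at Screening and read blinded by the PAC (Section 12.2), so most old lesions have a pre-treatment record. This weakens any worry about labels chosen after the fact, but not the gap in the definition.
- **One-subject sensitivity** is a feature of any exact test at this sample size. True; it matters here because the two sets can differ by one subject.

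A reader might also infer that (b) turns a carcinoma into a primary response. The documents do not support that firmly: the synopsis has such subjects treated surgically, and Table 2 makes outside curative treatment a non-response at subject level with no end date. Nor does (b) turn persistent HSIL into non-progression. Table 6 counts only worsening to cancer, so HSIL alone is non-progression under both sets.

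**Conclusion.** The point holds in a limited form. Read with Table 1, set (b) omits lesions present but not qualifying at baseline. It can therefore class as a responder a subject who fails footnotes 7 and 8 and Table 2, provided that the qualifying lesions have cleared, no new lesion is positive, and neither outside curative treatment nor an unscheduled biopsy has occurred.

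The consequence for the primary claim comes from leaving the decisive set unnamed. If (a) decides, the rule stays at 7 of 22 or 8 of 24 with the attained alpha shown. If (b) decides, the chance of declaring superiority when the rate under (a) is 15% rises to between 0.066 and 0.301 (n = 22) or between 0.039 and 0.234 (n = 24), for an assumed excess of 2% to 10%. These are conditional illustrations, not an estimate of the trial's false-positive rate.

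For carcinoma, the remaining gap is mainly in the non-progression endpoint. It is narrow, and one sentence would close it.

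**What to change.** 1. In Section 8.5.1, name set (a) as the decisive primary analysis, since it matches footnote 8 and Table 2, and label set (b) supportive. This also makes the single-hypothesis statement in Section 8.5.7 true.
2. In Sections 8.5.1, 8.5.2 and 8.5.9, define set (b) as lesions qualifying at baseline, new lesions, and any other baseline lesion whose tissue at evaluation is HPV-16/18 positive or shows AIS or carcinoma. Baseline HSIL of other types that stays HPV-16/18 negative, without AIS or carcinoma, remains outside (b).
3. State that AIS or carcinoma at any anal or peri-anal site is non-response in both sets, and do not split the non-progression endpoint by lesion set.
4. Reconcile Table 1 with the synopsis (Study Design and Efficacy Assessment) and Sections 3.0, 3.7 and 6.17 on which lesions are biopsied at Week 36.

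The cost of items 1 to 3 is wording. The set (b) response rate may be slightly lower than under the present definition. Item 4 has to be settled before the tissue needed for the revised set (b) can be assumed available at Week 36.

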8.5.2 SECONDARY ANALYSES

The secondary efficacy binary endpoints will be analyzed in the same manner as the primary hypothesis, but without the hypothesis test p-values. The efficacy time frame is defined in the same manner as for the primary endpoint. All of the efficacy binary endpoints will be analyzed in two ways: a) based on all lesions and b) based on qualifying and new lesions.

The anatomic extent endpoint will be analyzed by calculating the mean percent change in surface area and the mean percent change in number of lesions and associated 95% t-distribution based confidence intervals.

Post-baseline increases in Flow responses will be summarized with medians and 95% CIs. Valid samples for statistical analysis purposes will be those collected within 14 days of the specified visits. Baseline is defined as the last measurement prior to the first treatment administration.

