4. Determine the efficacy of three doses of VGX-3100 as measured by virologic clearance of HPV-16 and/or HPV-18 by intra-anal swab testing	4. Proportion of subjects with no evidence of HPV-16 and/or HPV-18 from intra-anal swab by specific HPV testing at Week 36
5. Determine the efficacy of three doses of VGX-3100 as measured by complete histopathologic regression of anal or anal/peri-anal HSIL to normal tissue	5. Proportion of subjects with no evidence ¹⁰ of anal or anal/peri-anal Low grade squamous intraepithelial lesion (LSIL) or HSIL (i.e. no evidence of AIN2, AIN3, PAIN2, PAIN3) on histology (i.e. biopsies or excisional treatment) at Week 36
6. Determine the efficacy of three doses of VGX-3100 as measured by histopathologic non-progression of anal or anal/peri-anal HSIL	6. Proportion of subjects with no progression ¹¹ of anal or anal/peri-anal HSIL to carcinoma from baseline to histology (i.e. biopsies or excisional treatment) at Week 36
7. Describe the efficacy of VGX-3100 for partial responders , as measured by reduction in the number of intra-anal and/or peri-anal qualifying lesion(s), as applicable and the reduction in size of peri-anal lesion(s) if present, and for whom the disease has not progressed according to Investigator judgment in subjects who did not have anal or anal/peri-anal HSIL lesion resolution at Week 36	7. Percent reduction in the number of qualifying ¹² intra-anal and/or peri-anal lesion(s), and the reduction in size of peri-anal lesion(s) as determined by the Investigator at Weeks 36, 64, and 88 compared to baseline ¹³ .
8. Determine the cellular immune response following dose 3 and compared to baseline	8. Flow Cytometry response magnitude at baseline and Week 15

9. Determine the efficacy of three doses of VGX-3100 with respect to histopathologic regression of anal or anal/peri-anal HSIL or virologic clearance of HPV-16 and/or HPV-18
	
9. Proportion of subjects with no histologic evidence of anal or anal/peri-anal HSIL by histology (i.e., collected via biopsy or excisional treatment) or no evidence of HPV-16/18 at Week 36 from intra-anal and/or peri-anal lesion tissue

---	---

⁹ Clearance of HPV-16 or HPV-18 is defined as being undetectable by PCR assay.

¹⁰ No evidence of anal or anal/peri-anal HSIL is defined as normal tissue or anal or anal/peri-anal LSIL.

¹¹ Progression is defined as advancement to carcinoma by histology according to the Pathology Adjudication Committee.

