8.6 SAMPLE SIZE/POWER

A sample of 24 subjects provides ~80% power to declare superiority over historical control, assuming the true proportion of subjects who achieve the primary endpoint is 40% for the treatment arm versus 15% for the historical control, and that 90% are evaluable at Week 36 from 1st dose.

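### Lesion number and size are averaged through Week 88 with no rule for lesions removed by non-study treatment, so the mean can show a reduction without a drug effect

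*Protocol*

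**What the plan says.** All references are to protocol version 3.0.

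- **Analysis.** Section 8.5.2: "The anatomic extent endpoint will be analyzed by calculating the mean percent change in surface area and the mean percent change in number of lesions", each with a t-based 95% interval. There is no comparator and no test.
- **Endpoint.** Synopsis secondary endpoint 7 and section 3.4 assess lesion number and peri-anal lesion size at Weeks 36, 64 and 88 against baseline. Objective 7 is aimed at subjects whose HSIL had not resolved at Week 36.
- **Removal is allowed.** For subjects with residual HSIL at Week 36 (Subgroup C), the Synopsis offers an option in place of dose 4: "Alternatively, the Investigator may instead choose to treat the subject with standard of care treatment (i.e. electrocautery, ablation, surgical excision"). Worsening may be treated in the same way at any time. Subjects with HSIL at Week 64 go to standard of care. All remain on study, and the Schedule of Events has anoscopy and photography at Weeks 64 and 88.
- **Binary endpoints.** Synopsis Tables 2 to 7 make non-study treatment of curative intent a non-response. They do not cover lesion number or size.
- **Which lesions.** The Synopsis endpoint reads "Percent reduction in the number of qualifying" lesions, and section 3.4 agrees. Section 3.3 attaches the word qualifying to size instead, and 8.5.2 restricts neither.
- **Baseline.** Synopsis footnote 13: "Baseline photographic imaging is defined as photographs obtained pre-biopsy at Screening, or post biopsy at Screening (for subjects with historical biopsy tissue"). Section 8.5.2: "Baseline is defined as the last measurement prior to the first treatment administration".

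**The concern.** Endpoint 7 is meant to show what VGX-3100 achieves in partial responders, and those are the subjects most likely to be offered excision or ablation. A lesion that has been cut out is absent at the next anoscopy. Unless the analysis says otherwise, its absence enters the mean as a reduction after VGX-3100. A single-arm trial has no control group in which the same artefact would appear and cancel. The sponsor dealt with this problem for the binary endpoints but not for this one.

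Two smaller ambiguities affect the same endpoint. There are two baseline definitions for size, and three texts that disagree on which lesions are counted.

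**Working it through.** **1. Number of subjects.** The only planning figure, in section 8.6, concerns the primary endpoint: "A sample of 24 subjects provides ~80% power to declare superiority over historical control". Its inputs are response rates of 40% and 15% and an evaluable share of 90%. The exact binomial test at one-sided 0.05 reproduces it: n = 24 with success at 8 or more responders gives power 80.8%; n = 21 with 7 or more gives 80.0%. No figure is stated for lesion number or size. What carries over is n = 24, or about 22 evaluable (0.9 × 24 = 21.6).

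**2. Removal with no drug effect.** Let k of n subjects have all counted lesions removed (−100%) and the others be unchanged (0%). Then

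- mean = −100·k/n
- SD = 100·√[k(n − k) / (n(n − 1))]
- 95% CI = mean ± t(0.975, n − 1)·SD/√n

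For k = 4 and n = 24: mean = −16.7; SD = 100·√(80/552) = 38.07; SE = 38.07/√24 = 7.77; t = 2.069; half-width = 16.1. The interval is −32.7 to −0.6.

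| Subjects treated | n = 24: mean (95% CI) | n = 22: mean (95% CI) |
|---|---|---|
| 2 | −8.3% (−20.3 to 3.6) | −9.1% (−22.1 to 4.0) |
| 4 | −16.7% (−32.7 to −0.6) | −18.2% (−35.7 to −0.7) |
| 6 | −25.0% (−43.7 to −6.3) | −27.3% (−47.5 to −7.1) |
| 12 | −50.0% (−71.6 to −28.4) | −54.5% (−77.1 to −31.9) |

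The protocol gives no share treated, so k is an assumption. If the mean is confined to subjects without resolution at Week 36, the denominator is smaller and the same k weighs more.

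**3. Recurrence.** If a fraction r of treated subjects is back at baseline by the visit, the mean becomes −100·(k/n)·(1 − r). Section 1.2 puts recurrence after surgery above 50%, without a time frame. At r = 0.5, 4 of 24 gives −16.7 × 0.5 = −8.3%, and 12 of 24 gives −25%.

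**4. Timing.** The Subgroup C option follows the Week 36 biopsy, so Week 36 can be affected only by earlier treatment for worsening. Week 64 can follow Subgroup C treatment. Week 88 can also follow treatment for HSIL found at Week 64.

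**5. Baseline for size.** The screening biopsy is typically 4 mm. If its whole area is subtracted from a round lesion of diameter D mm and nothing heals, the fraction removed is 16/D²: 64% at 5 mm, 16% at 10 mm, 4% at 20 mm. This is an upper bound. It applies only to subjects with a pre-biopsy photograph, only if footnote 13 governs, and only to peri-anal size. The biopsy must leave part of the lesion, so the count should not change.

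**6. Qualifying-only count.** Qualifying lesions are confirmed as HPV-16/18-positive HSIL (footnote 12), and both 8.5.2 and Table 1 name new lesions separately. A count confined to the baseline qualifying set can therefore stay level or fall, but cannot rise. As an illustration, take 22 subjects with 1 + Poisson(1) lesions each, and let lesions that disappear be replaced on average by equal numbers of new ones. At assumed turnover of 10%, 20% and 30%, the all-lesion mean change is about 0%, while the qualifying-only mean is −10%, −20% and −30%.

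**The case against.** The protocol nowhere says that measurements after removal are kept; it is silent. That is correct, and a reader should not infer a deliberate rule. But section 8.1 calls section 8 the formal statistical analysis plan, the visits continue, and 8.5.2 averages without exclusion. Followed as written, the plan includes those values.

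The calculation can be called contrived. The share treated has no source, and at 2 of 24 the interval includes zero. Scoring every removal at −100% ignores the stated recurrence rate. One of the two wordings of Subgroup C in the Synopsis already requires fewer lesions, so an unchanged count in the others would not fit it. These points limit the size and are why a range is shown; they do not change the direction.

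Three stronger readings are tempting and are not supported:

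- *The endpoint uses a pre-biopsy baseline that inflates the effect.* Footnote 13 allows post-biopsy photographs for historical tissue, and the share of such subjects is not given. The last-pre-dose sentence in 8.5.2 would remove the problem if it applies to lesions, but it stands in the flow-cytometry paragraph and its scope is unclear. A ruler measurement of outer dimensions may also be unaffected by a punch.
- *Counting only qualifying lesions is an error.* Following the baseline lesions is a defensible descriptive target, and new lesions do enter the binary endpoints. The defects are the inconsistent text and a count that cannot show worsening.
- *All three features bias towards benefit.* The baseline feature does so under only one of two readings, and never for number.

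**Conclusion.** The point holds for removal by non-study treatment. Under the plan as written, the Week 64 and 88 means can show a reduction with no drug effect, and Week 36 can do so only through earlier treatment for worsening. With zero true change and no recurrence, 4 treated subjects among 24 are enough for the interval to exclude zero, while 2 are not. Recurrence shrinks the shift in proportion. The share treated, complete removal and no change in the other subjects are assumptions; the documents fix none of them.

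The baseline conflict and the inconsistent use of qualifying are ambiguities to settle, not demonstrated biases. The endpoint is secondary, descriptive and untested. The primary endpoint has its own rule for non-study treatment, so the primary conclusion is unaffected.

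**What to change.** In section 8.5.2:

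1. State that lesions removed by non-study treatment of curative intent are not credited as reduction. At later visits use the last measurement before that treatment. As a sensitivity analysis, exclude post-treatment values. Exclusion should not be the main analysis, because it leaves a selected group at Weeks 64 and 88. Add a matching exception to section 8.5.8, which otherwise allows no imputation or replacement beyond adverse event dates.
2. Report the number of subjects so treated beside each mean.
3. Name one baseline for peri-anal lesion size for all subjects, preferably the Day 0 ruler measurement already scheduled, and align footnote 13 with it.
4. Make the Synopsis and section 3.4 agree with sections 3.3 and 8.5.2 on whether number is restricted to qualifying lesions. If it is, show the count of qualifying plus new lesions beside it.

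The cost is wording and programming; no visit or measurement is added. Treatment dates must be available to the analysis, as the binary endpoint rule already requires treatment to be identified. The sensitivity analysis will have fewer subjects at Weeks 64 and 88.
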